4.6 STUDY EARLY TERMINATION

The Sponsor may terminate the study prematurely according to certain circumstances, for example:

- a) ethical concerns,
- b) insufficient patient recruitment,
- c) when the safety of the patient is doubtful or at risk, respectively,
- d) alterations in accepted clinical practice that make the continuation of the investigation unwise,
- e) early evidence of benefit or harm of the experimental intervention.

The Sponsor may terminate the inclusion of patients at a study site at any time after the study initiation visit. Specific instances that may precipitate such termination are:

- a) multiple or severe CIP violations, or non-compliance without justification and/or repeated failure to follow remedial actions
- b) unauthorized use of the study device in another clinical study
- c) no patients have been enrolled
- d) inaccurate and/or incomplete data recording on a recurrent basis

In the event of termination of Investigator participation, all study materials, as applicable, must be returned to the Sponsor, unless this action would jeopardize the rights, safety or well-being of the patients. The Ethic Committee (EC/IRB) and Competent/Regulatory Authority (CA/RA), if applicable, should be notified.

5 STATISTICAL METHODS

5.1 HYPOTHESIS

The assumption is that the use of Alveogyl will allow to get a minimal residual pain at Day 7 post-treatment.

5.2 DETERMINATION OF SAMPLE SIZE

The determination of the sample size is based on the assumption that 92% of patients will have no pain or mild pain at Day 7 after the use of Alveogyl. The pain is assessed through a 10-point visual analogic scale (VAS) and a score strictly less than 4 is considered as mild pain or no pain [7].

The assumption of 92% is supported by the literature that reports a mean pain of 1.4 with standard deviation of 1.1 at Day 7, leading to a very large probability that patients have no pain / mild pain (VAS<4) at Day 7 [8].

The selected sample size is n=120, which will allow to estimate the proportion of no pain or mild pain with a satisfactory precision: the half-width of the 95% confidence interval of p=0.92 is 0.05 with n=113 patients and 7 patients are added in case of a few non-evaluable patients at Day 7 post-treatment.

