Follow-up(s)	
Patients will be evaluated at visit 1 – Day 0 and clinically followed at 7-day post-treatment (visit 2 – Day 7).
 
Some data will be collected at home, at Day 3 and Day 5: Pain VAS, painkiller use, and feeling of Alveogyl (clove) taste.

Study duration	
Patient enrolment will last 30 months (estimate).
 
Each patient's participation will last 8 days.
 
The entire study is expected to last 30.5 months.

Statistical analytic plan	
The assumption is that 92% of patients will have no pain or mild pain at Day 7 (primary outcome). This assumption is supported by the literature that reports a mean pain of 1.4 with standard deviation of 1.1 at Day 7, leading to a very large probability that patients have no pain / mild pain (VAS<4) at Day 7.
 
The sample size n=120 is based on the half-width (precision) of the 95% confidence interval of p=0.92: with n=113, the half-width will be 0.05 and 7 patients are added in case of a few non-evaluable patients.

Table 1: Schedule of Study Procedures

Study Phase	Visit 1	Patients' self-evaluation at home		Visit 2
TIMELINE	Day 0	Day 3	Day 5	Day 7
Informed Consent	X			
Review Inclusion/Exclusion Criteria	X			
Demographics/Medical History of interest	X			
Prior/Concomitant Medications of interest	X			
Clinical examination**	X			X
Pain evaluation based on VAS	X	X	X	X
Treatment with Alveogyl paste	X			
Evaluation of the presence of Alveogyl paste (via its clove taste) in the socket		X	X	X
Evaluation of painkiller use		X	X	X
Serious and non-serious adverse events assessment	X			X*
Device deficiency	X			X*

* Investigator will report at Visit 2 - Day 7 all safety issues (serious and non-serious adverse events and device deficiencies) which occur since Visit 1 -Day 0

** Including evaluation of the alveolus healing status, evaluation of the mucosa inflammation status, evaluation of bleeding status, and of the presence/absence of superinfection.

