5.4.3 Analysis of Primary endpoint

The primary endpoint is the binary variable (yes / no) defined as the VAS at Day 7 < 4 (i.e., "Yes" when VAS is <4, "No" when VAS is \geq 4).

It will be reported with a percentage and a 95% confidence interval (with the exact method) in the evaluable population.

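### The half-width of 0.05 that justifies the sample size is a normal-approximation figure; the exact interval planned for the primary analysis gives about 0.054 with 113 patients and an expected 0.052 with 120

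*Combined protocol and SAP*

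**What the plan says.** Section 5.2 starts from "the assumption that 92% of patients will have no pain or mild pain at Day 7". It then sets the size ("The selected sample size is n=120") and calls the result adequate, in that this number is one "which will allow to estimate the proportion of no pain or mild pain with a satisfactory precision". The support for that statement is that "the half-width of the 95% confidence interval of p=0.92 is 0.05 with n=113 patients", after which "7 patients are added in case of a few non-evaluable patients at Day 7 post-treatment". The statistical row of the protocol summary repeats it: "with n=113, the half-width will be 0.05 and 7 patients are added in case of a few non-evaluable patients". Neither place says how the interval is calculated.

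Section 5.4.3 does name a method for the primary endpoint, the yes/no variable VAS below 4 at Day 7: "It will be reported with a percentage and a 95% confidence interval (with the exact method) in the evaluable population". Nothing in the document connects this choice to the figure in section 5.2. Section 5.4 refers to a statistical analysis plan to be written separately.

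**The concern.** The half-width is the only argument given for the sample size, so it should describe the interval that will be reported. For a proportion near 0.92 and about 113 patients, the exact interval is wider than the normal-approximation interval and clearly asymmetric, with the longer arm below the estimate. If the 0.05 comes from the normal approximation, the protocol promises slightly more precision than its own analysis is likely to deliver. A symmetric plus-or-minus 0.05 also hides how far down the lower limit reaches. The study has a single arm, is estimation-only and is described as pivotal in India, so this interval is the primary result, and many readers will look first at its lower limit.

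**Working it through.** **Inputs.** Section 5.2 gives p = 0.92, 95% confidence, half-width 0.05, 113 evaluable patients and 120 in total (113 + 7). Section 5.4.3 gives the exact method in the evaluable population. One assumption is added: exact means Clopper-Pearson, the usual reading.

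**1. Reproducing the plan's figure.** The normal-approximation half-width is z·√(p(1−p)/n), so n = z²·p(1−p)/d².

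- n = 1.96² × 0.92 × 0.08 / 0.05² = 113.1.
- Half-width at n = 113: 1.96 × √(0.92 × 0.08 / 113) = 0.0500.

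This returns both of the plan's numbers. Other methods at n = 113 and p = 0.92 give:

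| Method | Half-width |
|---|---|
| Wald | 0.0500 |
| Wilson | 0.0511 |
| Agresti-Coull | 0.0530 |
| Wald with continuity correction | 0.0544 |
| Clopper-Pearson | 0.0545 (0.0544 at the whole count 104) |

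Of these, only plain Wald gives 0.050, so planning by Wald is inferred.

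**2. The exact interval at whole counts.** For x successes in n, the lower limit is the 0.025 quantile of Beta(x, n−x+1) and the upper limit is the 0.975 quantile of Beta(x+1, n−x). The half-width is half the distance between them.

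| Observed | Exact 95% CI | Half-width | Below | Above |
|---|---|---|---|---|
| 104/113 (92.0%) | 0.854 to 0.963 | 0.0544 | 0.066 | 0.043 |
| 110/120 (91.7%) | 0.852 to 0.959 | 0.0536 | 0.065 | 0.043 |
| 111/120 (92.5%) | 0.862 to 0.965 | 0.0514 | 0.063 | 0.040 |

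Wald at 104/113 has half-width 0.0499 and lower limit 0.870. The exact lower limit of 0.854 is 1.6 points lower.

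**3. Expected half-width.** Averaging over x ~ Binomial(n, 0.92):

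| n | Exact | Wald | P(exact half-width ≤ 0.05) |
|---|---|---|---|
| 113 | 0.0537 | 0.0492 | 31% |
| 120 | 0.0521 | 0.0478 | 37% |

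If p is 0.92, the stated precision is more likely to be missed than met, even with no patient lost.

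**4. Sensitivity to p.** At n = 120 the expected exact half-width is 0.057 for p = 0.90, 0.052 for 0.92, 0.049 for 0.93 and 0.043 for 0.95.

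**5. Could rounding explain it?** If any value up to 0.0549 counted as 0.05, Wald would need 1.96² × 0.92 × 0.08 / 0.0549² ≈ 94 patients. The number 113 follows only from a target of 0.0500.

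**6. Size needed for an exact 0.05.** At p = 0.92, about 130 evaluable patients bring the expected half-width to 0.0499, and about 133 bring the half-width at an observed proportion of 0.92 to 0.0499.

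**The case against.** The strongest reply is that the sentence is not false as printed. The half-width is given to two decimals, and 0.0544 also rounds to 0.05. Section 5.2 never says that the figure is exact, and planning with a simple formula before reporting an exact interval is not in itself a contradiction. The rounding point is true of the printed figure, but it does not account for the choice of 113, which requires a target of 0.0500.

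Second, nothing hangs on the difference, and it is smaller than the uncertainty about p. At n = 120 a true proportion of 0.93 already brings the expected exact half-width to 0.049. The literature figures cited in section 5.2 (mean 1.4, SD 1.1) point higher still: under a normal model, P(VAS < 4) = Φ((4 − 1.4)/1.1) = Φ(2.36) ≈ 0.99, for which the expected exact half-width at n = 120 is about 0.023. This stands as an argument about importance. The plan's precision statement is nevertheless made at p = 0.92, and if p were 0.90 the expected half-width would be 0.057.

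Third, exact is not defined. A mid-P interval gives 0.0508 at 104/113, 0.0502 at 110/120 and 0.0480 at 111/120, so the gap would nearly vanish. That is correct, and it is a reason to name the method. The separate analysis plan could do so, but the sentence in section 5.2 would still need to agree with it.

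Finally, the 7 additional patients might be thought to absorb the difference. Section 5.2 assigns them to non-evaluable patients, and even with all 120 evaluable the expected exact half-width is 0.052.

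**Conclusion.** The concern holds. The 0.05 with 113 patients is the normal-approximation value, and the exact interval in section 5.4.3 does not deliver it at the plan's own assumption. The shortfall in half-width is about 0.4 percentage points at 104/113 (0.0544 against 0.0500) and 0.2 points in expectation with 120 evaluable patients (0.0521 against 0.05). This rests on p = 0.92, on Clopper-Pearson as the meaning of exact, and on the inference that Wald was used for planning.

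The consequence is limited. The plan sets no test, performance goal or lower-limit threshold, the exact interval is valid, and 120 patients remain a reasonable number for estimation. The sample-size statement should be made consistent with the analysis; neither the design nor the analysis needs to change.

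**What to change.** Keep 120 patients and the exact method. Replace the precision statement in section 5.2 and in the protocol summary, for example with:

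> With 113 evaluable patients and about 92% observed (104/113), the exact (Clopper-Pearson) 95% confidence interval is about 85.4% to 96.3% (half-width about 0.054; 6.6 points below and 4.3 points above the estimate). If all 120 patients are evaluable, the expected half-width at p = 0.92 is about 0.052.

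Name Clopper-Pearson in section 5.4.3 and in the separate analysis plan as well, or, if another exact method is meant, name that one and recalculate. Merely labelling the present figure as a normal approximation would remove the ambiguity but would still not describe the interval to be reported.

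The cost is wording only: no additional patients and no change to the analysis. The stated precision becomes slightly less favourable. Only if the sponsor regards 0.05 as a firm requirement would the number have to rise, to about 130 to 133 evaluable patients; nothing in the plan indicates that it is.

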5.3 STATISTICAL CRITERIA OF TERMINATION OF THE STUDY

N/A. As this is a study with a device already in the market, it is not expected that the study device will do any harm to the patient that would justify an early termination of the study. Any unexpected serious adverse events will be reported and analysed by Septodont vigilance department.

5.4 STATISTICAL METHODS FOR PLANNED ANALYSES

A statistical analysis plan will be developed separately.

Quantitative data will be reported with n, n missing, mean, standard deviation (SD), median, minimum, maximum and 1st and 3rd quartiles.

Qualitative data will be reported as n, n missing and percentage (calculated over the non-missing data).

5.4.1 Analysis populations

Included population (intention-to-treat population - ITT): all included patients.

Evaluable population (per-protocol population - PPP): all patients from the included population with no exclusion criteria and with VAS available at Day 7.

5.4.2 Baseline Data

Baseline data will be described in the included population: demography, characteristics of the tooth extraction, clinical characteristics of the dry socket will be reported. The pain measured with VAS just before the treatment with Alveogyl and just after will be described as well as the clinical signs just after the placement of Alveogyl (local inflammation, bleeding).

The ease of use for the dentist will be described too.

In case the size of the evaluable population is much smaller than the included population (10% less), the description of baseline data of the patients will be performed also in the evaluable population.

5.4.3 Analysis of Primary endpoint

The primary endpoint is the binary variable (yes / no) defined as the VAS at Day 7 < 4 (i.e., "Yes" when VAS is <4, "No" when VAS is \geq 4).

It will be reported with a percentage and a 95% confidence interval (with the exact method) in the evaluable population.

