4.5.4 Patient completion/Withdrawal

Patients may withdraw from the study at any time without prejudice to their care. They may also be discontinued from the study at the discretion of the Investigator for lack of adherence to study treatment or visit schedules or AEs.

The Investigator may also withdraw patients who violate the study plan, or to protect the patients for reasons of safety or for administrative reasons. It will be documented whether each patient completes the clinical study. If the Investigator becomes aware of any serious, related adverse events after the patient completes or withdraws from the study, they will be recorded in the source documents and on the CRF.

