5.5 HANDLING OF MISSING DATA AND DROP-OUTS

No data will not be imputed, only available data will be used in the analyses.

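### The primary proportion is planned only for patients with a Day 7 VAS, with no imputation and no analysis of all included patients, so it may be biased upward

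*Combined protocol and SAP*

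**What the plan says.** - **Primary analysis (§5.4.3).** The endpoint is yes/no, Day 7 VAS below 4. On reporting: "It will be reported with a percentage and a 95% confidence interval (with the exact method) in the evaluable population". No other population is named for it.
- **Population (§5.4.1).** The evaluable set, which the protocol also calls per-protocol, is "all patients from the included population with no exclusion criteria and with VAS available at Day 7". An included (ITT) population is also defined, but the only analysis assigned to it is the baseline description in §5.4.2.
- **Missing data (§5.5).** The sentence opens with a double negative, but its second half is clear: "only available data will be used in the analyses".
- **Routes out of the study (§4.5.4).** Besides withdrawing, patients may be "discontinued from the study at the discretion of the Investigator for lack of adherence to study treatment or visit schedules or AEs".
- **Allowance for loss (§5.2).** The sample size is 113 evaluable patients, and "7 patients are added in case of a few non-evaluable patients at Day 7 post-treatment".
- **Related safeguards.** Counts of missing values are reported (§5.4), completion is documented for each patient (§4.5.4), and VAS by day is summarised on available observations (§5.4.4). If the evaluable population is 10% smaller than the included one, baseline data are described in it as well (§5.4.2).
- **SAP (§5.4).** "A statistical analysis plan will be developed separately". It is not among the documents, so this point concerns what the protocol itself fixes.

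**The concern.** A patient without a Day 7 score disappears from both numerator and denominator. That is harmless only if such patients would have succeeded at the same rate as those observed, and the protocol gives reason to doubt it. Discontinuation for adverse events is allowed, and §1.5.2 lists pain, infection and delayed healing among the anticipated events, so a discontinuation for an adverse event may be one for the very outcome being measured. §4.5.3 expects some patients to return early because of pain, and the items recorded at such a visit do not include a VAS. If those patients then miss Day 7, they have no primary outcome. If they attend, they stay in.

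The study has one arm and no performance goal or test, so its primary conclusion is this percentage and its confidence interval. The study is regarded as pivotal in India (§4.1) and is meant to support CE-marking under the MDR (§1.1). The exact interval covers sampling error only and says nothing about selective loss of Day 7 scores.

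**Working it through.** **Inputs.** Expected success proportion 0.92, half-width 0.05, 113 evaluable and 7 extra patients (§5.2); total 120 (§4.2.3); exact 95% interval (§5.4.3); 10% trigger (§5.4.2).

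**1. The plan's own figure.** n = z² p(1−p)/d² = 1.95996² × 0.92 × 0.08 / 0.05² = 113.09. The half-width at n = 113 is 0.0500, so the stated figure reproduces. 113 + 7 = 120, and the planned loss is 7/120 = 5.8%.

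**2. Result as planned.** 0.92 × 113 ≈ 104 successes. 104/113 = 92.0%, exact (Clopper-Pearson) 95% CI 85.4 to 96.3.

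**3. All 120 included patients.** If f of the 7 non-evaluable patients fail, the proportion is (111 − f)/120. The excess of the reported rate is 104/113 − (111 − f)/120.

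| Failures among the 7 | All included | Exact 95% CI | Evaluable minus all included (points) |
|---|---|---|---|
| 0 | 111/120 = 92.5% | 86.2 to 96.5 | −0.5 |
| 1 | 110/120 = 91.7% | 85.2 to 95.9 | +0.4 |
| 3 | 108/120 = 90.0% | 83.2 to 94.7 | +2.0 |
| 4 | 107/120 = 89.2% | 82.2 to 94.1 | +2.9 |
| 6 | 105/120 = 87.5% | – | +4.5 |
| 7 | 104/120 = 86.7% | 79.3 to 92.2 | +5.4 |

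Half failing (f = 3.5) gives 107.5/120 = 89.6%, an excess of about 2.5 points.

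**4. Break-even.** The excess is zero when the missing fail at the observed rate, 9/113 = 8.0%, that is 7 × 0.080 = 0.56 patients. One failure among the 7 is enough to make the reported rate too high.

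**5. The 10% trigger.** 10% of 120 is 12 patients. The planned loss of 7 does not reach it, and what it triggers is a baseline description, not an outcome analysis.

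**6. Larger loss (assumed; the documents give no rate beyond 7).** With about 92% success among those observed and all missing counted as failures:

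| Missing | Evaluable | All included | Gap (points) |
|---|---|---|---|
| 12 | 99/108 = 91.7% | 99/120 = 82.5% | 9.2 |
| 18 | 94/102 = 92.2% | 94/120 = 78.3% | 13.8 |

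**The case against.** **The direction is not established.** Discontinuation for missed visits need not relate to pain. Patients in pain may be more likely to come back, and pain-free patients may be the ones who skip Day 7. The lopsided bounds follow from any observed rate near 92% and are not evidence of direction. This stands, and it is why upward bias is called a risk and both bounds are requested.

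**The 5.4 points may overstate the gap.** A patient can also be non-evaluable because of an exclusion criterion and still have a Day 7 score. If, for illustration, 2 of the 7 were scored and succeeded at 92%, the worst case would be (104 + 1.84)/120 = 88.2%, a gap of 3.8 points. This is fair as a qualification. The maximum of 5.4 still applies if all 7 fail, whether unscored or ineligible but scored.

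**The effect is mostly within the stated precision.** Correct: six failures out of seven give 4.5 points, and only the all-failed extreme exceeds 5.

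**Readers could derive the bounds.** The Day 7 summary in §5.4.4 on available observations, with counts of missing values, gets them most of the way. It does not supply intervals, reasons for missingness, or the outcomes of ineligible patients with a score.

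**The SAP may deal with it, and there is no randomisation for ITT to protect.** The SAP could add the analysis, but nothing in the protocol commits it to do so, and §5.5 points the other way. With no randomisation there is also no comparator in which selective loss could show itself.

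**Conclusion.** The concern holds and should be fixed. The protocol defines a population of all included patients and never uses it for the primary result, which is restricted to patients with a Day 7 score and has no sensitivity analysis. At the plan's own allowance of 7 in 120, the reported proportion could be up to 5.4 points too high and at most 0.5 too low, with about 2.5 points too high if half of the 7 fail. These are bounds, not predictions. They rest on 104 successes in 113 and on losses no larger than the 7 allowed for.

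Confidence is high on what the text provides. The direction of any bias is plausible but not shown. No pass/fail decision changes. What is at stake is how far the headline estimate of an uncontrolled study can be trusted.

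**What to change.** Keep the evaluable analysis in §5.4.3 and add text along these lines:

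> A mandatory sensitivity analysis will report the proportion with exact 95% CI in all included patients, (a) counting a missing Day 7 VAS as VAS ≥ 4 and (b) counting it as VAS < 4. Patients outside the evaluable population who have a Day 7 VAS keep their observed value. Both results are shown beside the evaluable result, with the number of patients without a Day 7 VAS by reason.

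In §5.5, exempt this sensitivity analysis from the no-imputation rule and remove the double negative. Carry the same text into the separate SAP before the data are reviewed.

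The cost is wording in two sections and one extra table, with no new outcome data. Completion is already documented per patient; a reason field may be needed if the CRF, which is not in the documents, lacks one. The drawback is that result (a) may look less favourable and is biased low unless every missing patient failed. It should therefore be presented as a bound and not as the main estimate.

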4 INVESTIGATIONAL PLAN

4.1 STUDY DESIGN

ALVE study is a clinical investigation assessing Alveogyl performance and safety in patients with post-extraction dry socket. The study will take place in India and in France where the study device is already marketed.

In India, the study is regulatorily considered as a pivotal clinical study in accordance with the Indian regulation.

In France – European Union, the study is regulatorily considered as an observational, post-market clinical follow-up study with additional non-invasive and non-cumbersome procedures: the clinical

investigation is under the category “Other Investigation (Case 1: Clinical Investigation Post-Market Clinical Follow-Up)” in accordance with the European Medical Device Regulation (EU MDR).

Management of dry socket application protocol is at the discretion of the Investigator. Patients treated with the study device will be screened and eligible patients will be included in the study after obtaining their consent.

The primary outcome will be pain assessed by Visual Analog Scale (VAS) for adults at 7 days post-treatment. VAS is a 10-point line from “no pain” (0 point) to “worst imaginable pain” (10 points). A corresponding scale will be used for children as appropriate.

Additionally, patients will self-evaluate their pain level, their painkiller use and the feeling of Alveogyl (clove) taste at day 3 and day 5 at home.

All data will be recorded in either paper or electronic Case Report Form (CRF) and monitored by the Sponsor’s designee.

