4.2.3 Number of investigational sites and patients estimated

120 patients will be enrolled in the clinical study.

The clinical study will be conducted at approximately 10 investigational sites in India which should recruit about 90 patients, and at 2 sites in France which should recruit about 30 patients.

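### The primary exact interval and the 0.05 precision assume independent patients; with about 12 sites, coverage of the 95% interval would fall appreciably below nominal if the intra-site correlation were about 0.05 or more, and no site display or sensitivity interval is planned

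*Combined protocol and SAP*

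**What the plan says.** Section 5.4.3 defines the endpoint: "The primary endpoint is the binary variable (yes / no) defined as the VAS at Day 7 < 4". It gives the whole primary analysis in one sentence: "It will be reported with a percentage and a 95% confidence interval (with the exact method"), in the evaluable population.

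Section 5.2 sizes the study on precision alone, "based on the assumption that 92% of patients will have no pain or mild pain at Day 7 after the use of Alveogyl". It then states that "the half-width of the 95% confidence interval of p=0.92 is 0.05 with n=113 patients and 7 patients are added" for non-evaluable patients, which gives 120.

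Section 4.2.3 plans "approximately 10 investigational sites in India which should recruit about 90 patients", plus 2 sites in France with about 30. That is about 9 patients per Indian site and 15 per French site. No cap per site is given.

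Section 4.1 states: "Management of dry socket application protocol is at the discretion of the Investigator". Section 4.5.1 repeats this in its Note 1, but also says that placement follows the IFU and lists the steps. Section 1.5.3 likewise says that treatment follows the IFU.

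Sections 5.4 to 5.5 mention no site or country term, no by-site or by-country table, and no design effect. Section 5.4 announces a separate SAP, which is not among the documents.

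**The concern.** An exact binomial interval has its stated coverage when patients are independent and share one success probability. Here patients are grouped by site, and preparation of the socket and application may vary between investigators. There is no control arm, so differences between sites do not cancel in a comparison; they enter the single pooled rate directly.

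If results are to be carried over to practice beyond these sites, variation between sites adds to the variance of that rate, and a binomial interval does not count it. The study is described as pivotal in India and is meant to support CE-marking under the MDR. This interval is its main inferential output, and "The selected sample size is n=120, which will allow to estimate the proportion of no pain or mild pain with a satisfactory precision" is the only justification for its size. If the precision is overstated, readers will trust the rate more than the data allow, and nothing in the planned output would reveal it.

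**Working it through.** **Inputs.** From the documents: p = 0.92, n = 113 evaluable, half-width 0.05 and the 95% level (5.2); the exact method (5.4.3); about 10 + 2 sites with about 90 + 30 patients (4.2.3). Assumed: ICC from 0.01 to 0.10, because the documents give none.

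**1. The plan's own figure.** The normal approximation for independent patients gives n = 1.96² × 0.92 × 0.08 / 0.05² = 113.09. At n = 113 the half-width is 1.96 × √(0.92 × 0.08 / 113) = 0.0500. The stated figure reproduces.

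**2. The method actually planned, no clustering.** The Clopper-Pearson interval for 104/113 (92.0%) is 85.4% to 96.3%. Its half-width is (0.963 − 0.854)/2 = 0.054, and the lower arm is 0.066. About 130 evaluable patients would be needed for an exact half-width of 0.05.

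**3. Design effect.** DE = 1 + (m_w − 1) × ICC, with m_w = Σm²/Σm. Scaling the planned split to 113 gives five sites of 8, five of 9 and two of 14, so m_w = (5×64 + 5×81 + 2×196)/113 = 1117/113 = 9.9. Effective n = 113/DE. The normal-approximation half-width is 0.0500 × √DE.

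**4. Coverage.** Beta-binomial simulation with true p = 0.92 and 100,000 runs per case, using the planned pooled Clopper-Pearson interval.

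| ICC (assumed) | DE | Effective n | Normal-approx. half-width | Exact interval at effective n | Coverage of planned interval |
|---|---|---|---|---|---|
| 0 | 1.00 | 113 | 0.050 | 85.4% to 96.3% | 96.5% |
| 0.01 | 1.09 | 104 | 0.052 | 85.0% to 96.4% | 95.6% |
| 0.02 | 1.18 | 96 | 0.054 | 84.7% to 96.6% | 94.8% |
| 0.05 | 1.44 | 78 | 0.060 | 83.6% to 96.9% | 92.0% |
| 0.10 | 1.89 | 60 | 0.069 | 82.0% to 97.4% | 87.6% |

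Using the site sizes for 120 enrolled patients instead, m_w = (10×81 + 2×225)/120 = 10.5, and the half-widths for ICC 0.02 to 0.10 become 0.055 to 0.070.

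**5. Uneven recruitment.** With no cap, a skewed split (sites of 2 to 25, m_w = 14.5) gives coverage of 95.2%, 93.9%, 89.8% and 83.4% at ICC 0.01, 0.02, 0.05 and 0.10.

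**6. What these ICCs mean.** The between-site SD of the true success rate is √(ICC × 0.92 × 0.08). That is √(0.02 × 0.0736) = 0.038, √(0.05 × 0.0736) = 0.061 and √(0.10 × 0.0736) = 0.086. So an ICC of 0.05 corresponds to an SD of about 6 percentage points.

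**The case against.** The case against is substantial, and much of it stands.

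- **Small site effects do no harm to coverage.** A reader might infer that the interval is too narrow whenever sites differ. It is not: the exact method starts at 96.5%, and that reserve absorbs an ICC up to about 0.02 under the planned split.
- **The lower limit is less affected than two-sided coverage suggests.** A reader might infer that the lower limit is simply too high. In simulation, the chance that it exceeds the true 0.92 (nominal 2.5%) is 1.7% at ICC 0, 2.3% at 0.02, 3.8% at 0.05 and 5.8% at 0.10. Roughly half of the lost coverage is at the upper limit.
- **The size is assumed.** The documents contain no data on site differences. They also bound the investigator's discretion by the IFU, so practice is not wholly free. Variation remains possible, because the same section keeps the discretion.
- **It depends on the target of inference.** If the conclusion is confined to these sites as fixed strata, the variance of the pooled rate is Σm_i p_i(1 − p_i)/n², which is at most p(1 − p)/n. Site differences then do not make the interval too narrow. The documents do not say which target is meant; use for registration points to wider practice.
- **A site-clustered interval is itself unstable.** With about 9 expected failures over 12 sites, the estimated design effect runs from about 0.55 to 2.08 (5th to 95th percentile) at a true ICC of 0.02, and is below 1 in about 43% of trials. This stands against making it the primary result.
- **The separate SAP may already cover this.** That cannot be checked here.

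What remains is that independence is neither stated nor examined in the text available, and that the stated precision is optimistic at any positive ICC.

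**Conclusion.** The point holds in a limited form. The interval in 5.4.3 and the precision in 5.2 rest on independent patients, in a design with about 12 sites and partly discretionary application. If sites are a sample of wider practice, coverage of the planned 95% interval is about 92% at an ICC of 0.05 and 88% at 0.10 with the planned split, and lower if recruitment is skewed. At 0.02 or less there is no material problem with coverage. These figures rest on an assumed ICC and a beta-binomial model.

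The precision statement needs correction in any case. The 0.05 does not come from the planned method, which gives 0.054 without clustering. At an ICC of 0.02 or less, that gap is as large as the clustering effect.

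A reader might also infer an inflated false-positive risk, or a need to base the conclusion on a wider interval. The documents support neither: they set no test, margin or success threshold, and the design effect would be too poorly estimated to replace the primary result. This is an inexpensive improvement to reporting, not a flaw that invalidates the analysis.

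**What to change.** **In 5.4.3 (and the separate SAP):**
- Keep the pooled exact 95% interval as the primary result.
- Add the number and proportion with VAS below 4 at Day 7 by site and by country.
- Pre-specify a site-clustered sensitivity interval, reported beside the primary one. One choice is Korn-Graubard: Clopper-Pearson with the effective sample size, capped at the actual n so that it never narrows the exact interval. In simulation such a capped interval restores coverage to about 95% at ICC 0.05 and 94% at 0.10.

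**In 5.2:** state that 0.05 is a normal-approximation half-width for independent patients; that the planned exact interval at 104/113 is 85.4% to 96.3% (half-width 0.054); and that site correlation would widen it further, with a normal-approximation half-width of about 0.054 to 0.070 for assumed ICCs of 0.02 to 0.10.

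**Cost:** a few lines of text, one table and one extra calculation, with no new patients, visits or data. The design effect will be imprecise with 12 sites and about 9 failures, so the clustered interval should be labelled a sensitivity analysis.
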